We aim to conduct a single-center randomized controlled trial to measure the impact of physical activity through virtual reality video games on the motor and cognitive performance of youth with MS. Through such a home-exercise program coupled with patient online behavior counseling, we hypothesize that we can significantly impact subjective and objective measures of disease disability in this MS age population.

Objectives

Primary objective: to assess the impact of a virtual reality video (VR) game exercise program on **objective cognitive assessments in youth with MS** (measures outlined below). The **null hypothesis** for this study is that there is no difference in the **Brief Cognitive Assessment for MS** in cognitive disability of youth with MS between those enrolled in a 6-month VR active video game program and those with routine follow-up care. The alternative hypothesis is that there is a difference in measures of cognitive disability between the two groups (two-sided hypothesis).

Secondary objectives:

- To determine the impact of VR physical activity on subjective measures of cognitive, physical and psychosocial disability in youth with MS
- To determine the impact of VR physical activity on the 6-Minute Walk Test (6MWT).

- To determine the number of clinical relapses and new T2 MRI lesions (brain)
- To determine the **safety** of implementing a VR active video game program at home
- To evaluate the effect of VR exercise programs on overall behavior towards physical activity and health promotion in youth through self-report questionnaires

Study Design

- **Single-center, single blinded, randomized controlled trial** comparing a 6-month VR active video game intervention with standard management of physical activity in youth with MS.
- Each participant will be randomly allocated to either the intervention group or the control group for a **period of 6-months** with pre- and post- assessments performed at onset, 3 months, 6 months and 12 months follow-up.
- The study will be conducted over one year with 6 months of intervention. Each group will include 12 subjects (**total subjects = 24**).
- The Microsoft VR active game program will consist of 3 weekly sessions of 45 minutes each combining 3 different types of exercise (cardiovascular and strength with 'Box VR', flexibility with 'Beat Saber', coordination with 'The Climb').

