- The subjective assessments will be mailed to the participants or given when seen in clinic. Study staff will perform the 6MWT at the time of a routine clinic visit and will require no additional costs.
- The three cognitive assessments per subject will be carried out by a qualified neuropsychologist or neurologist and will be performed at the time of a routine clinic visit.

Data and Safety Monitoring

- During the course of study participation, subjects might experience an adverse event related to the physical activity or to their underlying MS. These events might include falls, musculoskeletal injuries, neurological symptoms suggestive of a clinical relapse, or any other physical or psychological cause of distress. These events will be documented by participant self-reports and contacting study personnel. They will be graded from 1 to 3 according to their degree of severity with 1 = mild, no interference with daily activities, 2 = moderate, some interference with daily activities and 3 = severe, significant interference with daily activities and requiring medical intervention.
- The research team will perform a **periodic review of adverse events** recorded once every 2 months as well as an assessment of adherence to the exercise programs and any other concerns raised by the research team or the participants.
- In the event of a clinical relapse or worsening of a participant's neurological symptoms, the research team will promptly inform the MS specialist in charge of that participant's care. Subject's participation in the intervention group will cease.

Statistics

- Statistical analysis will be performed using the software program **Stata version 15**.
- Descriptive numerical or graphical summaries will be used for demographic and clinical characteristics of the sample population at baseline. Independent samples t-tests and chi-square tests will be done to assess differences between intervention and control groups on pre-trial and post-trial assessments. Only participants who completed the 6-month exercise program will be included in the analysis of the intervention group but missing data will be noted. Paired sample t-tests and chi-square tests will be conducted to determine differences in pre-trial and post-trial assessments within each group. If data reveals a skewed distribution, Kruskall Wallis tests will be used for continuous variables. All tests will be conducted using an alpha = 0.05 level of statistical significance.

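### The one fallback named for skewed scores, Kruskal-Wallis, is not limited to between-group comparisons, and no paired rank test is named for within-group change

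*Combined protocol and SAP*

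**What the plan says.** The Statistics section names three things in order.

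- Between arms: "Independent samples t-tests and chi-square tests will be done to assess differences between intervention and control groups on pre-trial and post-trial assessments".
- Within each arm: "Paired sample t-tests and chi-square tests will be conducted to determine differences in pre-trial and post-trial assessments within each group".
- Directly after the within-arm sentence: "If data reveals a skewed distribution, Kruskall Wallis tests will be used for continuous variables".

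The section closes the list with "All tests will be conducted using an alpha = 0.05 level of statistical significance". No signed-rank or sign test, transformation, permutation or bootstrap method appears in it. It does not say how skew is to be judged, or whether on raw scores or on pre/post differences.

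Study Design gives the size: "Each group will include 12 subjects". For the intervention arm the number of pairs may be lower, because "Only participants who completed the 6-month exercise program will be included in the analysis of the intervention group". The hypotheses under Objectives are two-sided and compare the two arms.

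**The concern.** Kruskal-Wallis assumes independent samples. Between the two arms that is met, and with two groups the test is the rank-sum test. Within an arm it is not met, because the pre and post scores come from the same people. The plan recognises this for the t-test but not for the fallback.

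Either reading of the fallback sentence leaves a gap. An analyst who follows it as written runs an unpaired test on paired scores. An analyst who takes it to mean between-arm comparisons only has no stated method for skewed within-arm data. At stake are the within-arm pre/post results: a real change in a small arm could be reported as no change.

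**Working it through.** **Inputs from the documents.** 12 per arm (Study Design); two-sided hypothesis (Objectives); alpha 0.05, paired t-test and Kruskal-Wallis fallback (Statistics). The plan gives no power, SD, effect size or correlation, so there is no figure of its own to reproduce.

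**Assumptions, not in the documents.** Log-normal scores with log-SD 0.5 (moderate skew) or 1 (strong skew); pre/post correlation r = 0.5, 0.7, 0.9 on the log scale; a 0.5 SD shift. Positive correlation is plausible, and Study Procedures cites good repeatability for the walk test, but that does not fix a six-month correlation.

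**Step 1: between arms.** On a test data set, two-group Kruskal-Wallis and the asymptotic rank-sum test without continuity correction both give p = 0.2253. The fallback is valid there.

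**Step 2: why pairing matters.** With n = 12 and N = 24, H = (W − n(N+1)/2)² ÷ (n²(N+1)/12) = (W − 150)² ÷ 300, where W is the rank sum of the pre scores. The divisor 300 is the variance of W for independent samples. Positive correlation makes the true variance smaller, so H is too small and the test rejects too seldom. The exact signed-rank test on 12 pairs rejects when the smaller rank sum is 13 or less, with true size 0.0425.

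**Step 3: Kruskal-Wallis used every time** (100,000 simulations per setting, 12 pairs; entries in % at r = 0.5/0.7/0.9).

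| Setting | Kruskal-Wallis | Paired t | Signed-rank |
|---|---|---|---|
| No change, moderate skew | 1.08/0.24/0.01 | 4.45/4.31/4.26 | 4.28/4.22/4.16 |
| No change, strong skew | 1.06/0.27/0.01 | 3.09/3.04/2.94 | 4.28/4.24/4.28 |
| Log-scale shift, moderate | 15.1/11.7/7.9 | 30.2/45.8/87.9 | 30.0/46.0/89.3 |
| Log-scale shift, strong | 15.0/11.8/7.9 | 19.7/29.9/63.8 | 28.0/42.6/85.3 |
| Additive shift, moderate | 26.3/24.2/21.8 | 39.0/55.9/90.2 | 39.2/56.3/90.6 |
| Additive shift, strong | 70.6/72.6/76.5 | 52.5/65.7/87.3 | 62.5/75.2/93.0 |

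At r = 0 Kruskal-Wallis holds about 5%, so the effect needs positive correlation. With 9 pairs (assumed dropout) and the log-scale shift, across both levels of skew, power is 5–11% for Kruskal-Wallis, 14–73% for paired t and 20–74% for signed-rank.

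**Step 4: the switch is conditional.** The fallback applies only if skew is found. Suppose, as a further assumption, that a 5% Shapiro-Wilk test on baseline scores decides. It flags about 30% of samples at moderate skew and about 70% at strong skew. If the flag were independent of the test result, overall power at moderate skew would be:

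- r = 0.5: 0.30 × 15.1 + 0.70 × 30.2 = 25.7%
- r = 0.7: 0.30 × 11.7 + 0.70 × 45.8 = 35.6%
- r = 0.9: 0.30 × 7.9 + 0.70 × 87.9 = 63.9%

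Direct simulation of the switch, log-scale shift (repeat runs differ by up to about two points of power):

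| Skew | Type I error | Power with switch | Paired t | Signed-rank |
|---|---|---|---|---|
| Moderate | about 3.5% | about 26/37/65% | about 30/45/89% | about 30/46/89% |
| Strong | about 1–2.4% | about 17/19/27% | about 20/30/64% | about 28/43/85% |

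The loss against paired t at moderate skew is 30 − 26 = 4, 45 − 37 = 8 and 89 − 65 = 24 points. At strong skew it is 20 − 17 = 3, 30 − 19 = 11 and 64 − 27 = 37 points.

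**Step 5: raw scores or differences.** A log-normal score with log-SD 0.5 has skewness (e^0.25 + 2) × √(e^0.25 − 1) = 3.284 × 0.533 = 1.75. With no change, the pre/post differences have skewness 0. The assumed Shapiro-Wilk check then flags 29–30% of baseline samples but 15–18% of samples of differences. A paired test depends on the differences.

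**The case against.** The plan never says that Kruskal-Wallis will be run on paired scores. Its authors specified paired t-tests, so they knew of the pairing and may have meant the fallback as shorthand for the comparison between arms, where it is valid. That reading is possible, but the sentence does not say it, and it still leaves skewed within-arm data without a method.

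The figures for Kruskal-Wallis used every time overstate what the plan would produce, since the switch is conditional. This stands: at moderate skew the overall error rate is about 3.5%, not 1% or less, and at r = 0.5 little power is lost.

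The direction is not universal either. With an additive shift at strong skew, Kruskal-Wallis beats signed-rank at r = 0.5 (70.6% v 62.5%) and beats paired t at r = 0.5 and 0.7. This also stands. The documents do not show that any of the seven instruments will be skewed, so the fallback may never be used.

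Signed-rank is no cure for skewed differences. With centred log-normal differences, 12 pairs and a true mean change of zero, it rejects 7.2% of the time at log-SD 0.5 and 16.9% at log-SD 1 (paired t 7.6% and 15.3%). It is proposed because it respects the pairing, not because it removes that problem.

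**Conclusion.** The point holds as a minor defect in the wording of a rule. Followed as written, the fallback puts an independent-samples test on paired scores; read narrowly, it leaves a gap. A better rule costs almost nothing.

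Once the fallback is triggered, type I error is about 1% or less at r of 0.5 and above, and power for a log-scale shift is about 15/12/8%. Over the whole conditional procedure the loss is small at r = 0.5 and large at r = 0.9. All sizes rest on the assumed log-normal shape, shift, correlation and skew check. None of these is in the documents.

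A reader might infer three stronger things that the documents do not support. First, that the trial's main result is compromised: the hypothesis is between arms, where Kruskal-Wallis is valid. Second, that the rule could manufacture a benefit within an arm: with positive correlation, ignoring the pairing makes the test conservative. Third, that the within-arm error rate always falls far below 0.05: under the assumed switch at moderate skew it does not.

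**What to change.** In the Statistics section, limit Kruskal-Wallis (equivalently, rank-sum) to comparisons between the two arms. For within-arm change, keep the paired t-test, judge its suitability on the pre/post differences and not the raw scores, and name Wilcoxon signed-rank as the rank-based fallback in place of Kruskal-Wallis.

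The cost is one or two sentences. The tests are standard Stata commands, and no extra data or visits are needed.

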- To assess the impact of the VR exercise program, a series of subjective and objective assessments will be performed prior to onset, at 3 months, upon completion at 6 months and at 12 months follow-up. These assessments are detailed in the section 'Study procedures' below.
- **Assessment of safety** will be conducted throughout the intervention and will consist of self-reported incidents that occur during the exercise sessions, including falls or physical injuries. These events will be recorded at 1 month, 3 months and 6 months from onset by the investigators.
- **Assessment of adherence** to the program will be documented throughout the study via anonymized exercise logs provided by Microsoft that will monitor participation and overall performance for each game. Microsoft will also provide customer service for any technical difficulties with the VR headsets provided.
- **Personal sessions** with each participant in the intervention group will be conducted via phone calls to educate them on the importance of exercise and assess for any difficulties to adhere to sessions. They will take place at 1 month, 3 months and 6 months. Furthermore, a survey questionnaire will be given to all participants enrolled in the intervention group at the 6-month follow-up time to determine the degree of incorporation of physical activity into their daily life following completion of the study.

Study Population

- Inclusion criteria: (1) **age between 15-25 years**, (2) **confirmed diagnoses of Pediatric-Onset MS (<18 years)** according to the 2017 revised McDonald criteria (relapsing-remitting), (3) **Expanded Disability Status Scale (EDSS) ≤ 5.0**, (4) **relapse free for the past 30 days**, (5) **no contraindications to physical activity**, including pregnancy (6) no history of visual provoked seizures and (7) participant and parent (if between 15 and 18 years of age) **written informed consent**.
- The participants will be recruited through the neurology clinic in Houston using phone, email or postal communications. People who are interested in taking part will be contacted by the research team via phone or email and explained the study in detail. If the selection criteria are met, informed consent forms and participant information leaflets will be sent via post or email, or obtained during a routine clinic visit.

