- Participants will be **randomly allocated in blocks** to either the intervention or control group, and the allocation group will be **concealed from the study personnel** that are analyzing the data.

Study Procedures

- Subjects in the intervention group will receive a Samsung Windows Mixed Reality headset with motion controllers that links to their PC/laptop. They will be given 3 different VR video games (Box VR, Beat Saber and The Climb) at onset. They will be instructed to play a minimum of 3 sessions per week, one session on each game, for the first 3 months. They will have the possibility of dropping one game for the remaining 3 months but maintaining a minimum of 3 sessions per week. Each session will last 45 minutes. They may play more than 3 sessions per week but will be required to document additional time.
- **Exercise logs** will be provided to document weekly sessions for monitoring adherence. Participants in both groups will be asked to document any sport activities performed during the study period, with an estimate of duration per week and type of activity, to account for physical activity done outside of the active intervention. This will be recorded during the 6-month intervention period.
- The intervention group will also receive two **education discussion sessions** on the benefits of exercise for people with MS. The investigator MS specialists will conduct these sessions either by phone or at the time of a clinic visit and will also discuss difficulties encountered by participants with adherence.
- A neuropsychologist or MS specialist will perform an **objective cognitive assessment** at the time of enrollment, at 6 months and at 12 months follow-up, consisting of the **Brief International Cognitive Assessment for MS (BICAMS)**, which includes three subtests:
 - **Symbol Digit Modalities Test (SDMT)**, a measure of sustained attention, working memory and information processing speed
 - **California Verbal Learning test – II (CVLT-II)**, a measure of verbal memory (immediate recall) including the first 5 recall trials
 - **Brief Visuospatial Memory Test (BVMT) - Revised**, a measure of visuo-spatial learning and delayed recall, using the first 3 recall trials

The battery takes 15 min to complete, requires no specialist equipment and no specialist expertise in cognitive assessment.

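### The single primary BICAMS hypothesis has three subtests, two post-baseline visits and no success rule; if any one subtest at p<0.05 counts, the 6-month false-positive rate is about 11-14% (assumed subtest correlation 0 to 0.7)

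*Combined protocol and SAP*

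**What the plan says.** The primary null in Objectives is a single statement about the BICAMS battery. It sets the contrast as "between those enrolled in a 6-month VR active video game program and those with routine follow-up care". The alternative that follows is two-sided and speaks of measures in the plural.

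Study Procedures describes BICAMS as a battery "which includes three subtests": SDMT, CVLT-II and BVMT-R. It is given "at the time of enrollment, at 6 months and at 12 months follow-up", so there are two post-baseline visits.

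Statistics plans independent-samples t-tests of "differences between intervention and control groups on pre-trial and post-trial assessments", then paired tests within each arm, with a rank-based alternative for skewed data. The only error-rate statement is "All tests will be conducted using an alpha = 0.05 level of statistical significance".

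The meaning of post-trial is not fixed. One bullet in Study Design describes the trial "with pre- and post- assessments performed at onset, 3 months, 6 months and 12 months follow-up", which makes every later visit a post-assessment. A later bullet lists the visits as "prior to onset, at 3 months, upon completion at 6 months and at 12 months follow-up", which sets the end of intervention apart from follow-up.

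**The concern.** One null is to be judged from three subtest scores at 6 months, and possibly three more at 12 months, each tested at 0.05. Nothing says how the p-values combine into one answer. The plan does not say that one significant subtest is enough, that two are needed, or that all three are needed. Nor does it define a total or composite score.

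The same results could therefore be reported as positive or negative according to a rule chosen once they are known. A reader could not tell which error rate applies to the primary claim. A per-test level of 0.05 does not give a 5% error rate for the primary hypothesis unless exactly one test decides it.

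**Working it through.** **Inputs from the protocol.** Per-test alpha 0.05 (Statistics); two-sided (Objectives); three subtests at 6 and 12 months (Study Procedures); 12 per arm, 24 in total (Study Design). The plan states no familywise error rate, power, effect size or SD, so it has no derived figure to reproduce. A single test at 0.05 simply returns 5%.

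**Assumed inputs.** Correlations between subtests and between visits are not given. Subtest correlations of 0 to 0.9 and visit correlations of 0.5 to 0.8 were tried.

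**Step 1: independent subtests, 6 months only.**
- Any one of three: 1 − 0.95³ = 14.3%.
- At least two of three: 3 × 0.05² × 0.95 + 0.05³ = 0.7%.
- All three: 0.05³ = 0.01%.

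**Step 2: correlated subtests.** Multivariate-normal trials were simulated under the global null, with 12 per arm and pooled two-sided t-tests at 0.05. There were 400,000 trials per setting for the any-one and all-three columns and 100,000 for the middle column.

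| Assumed subtest correlation | Any one of three | At least two | All three |
|---|---|---|---|
| 0 | 14.2% | 0.7% | 0.01% |
| 0.3 | 13.7% | 1.2% | 0.1% |
| 0.5 | 12.7% | 2.1% | 0.3% |
| 0.7 | 11.1% | 3.1% | 0.8% |

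At correlations of 0.8 and 0.9 the any-one rate is 10.0% and 8.6%, and the all-three rate is 1.3% and 2.1%.

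**Step 3: unequal numbers analysed.** Statistics restricts the intervention arm to completers. With an assumed 9 completers against 12 controls, the any-one rate is still 11-14% over correlations 0 to 0.7. The inflation hardly depends on sample size.

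**Step 4: if 12 months also counts as post-trial.** Any one of six independent tests gives 1 − 0.95⁶ = 26.5%. By simulation the rate is 17.0% (subtest correlation 0.7, visit correlation 0.8) to 24.0% (0.3 and 0.5).

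**Step 5: error rate after the fix, 6 months only.** One composite tested once gives 5.0-5.1% by simulation (60,000 trials per setting, baseline standardisation, assumed baseline-to-6-month correlation 0.6). Holm over the three subtests gives 4.0-4.8% under the global null. As a check, Bonferroni with independent subtests gives 1 − (1 − 0.05/3)³ = 4.9%.

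**Step 6: power cost.** Effects detectable at an assumed 80% power, from the noncentral t distribution for an unadjusted t-test:

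| Analysed | alpha 0.05 | alpha 0.05/3 (first Holm step) |
|---|---|---|
| 12 vs 12 (df 22) | 1.20 SD | 1.41 SD |
| 9 vs 12 (df 19) | 1.30 SD | 1.55 SD |

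Simulated power with 12 per arm, subtest correlation 0.3-0.7 and 40,000 trials per setting:
- All three subtests shift by 1.0 SD: composite 74-89%, against 66-77% for Holm to find at least one.
- Only one subtest shifts, by 1.2 SD: composite 18-25%, against about 65% for Holm.

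**The case against.** The strongest reply is that the plan never says one subtest is enough. The null is worded for the battery, and a rule of two or three subtests would run below 5%. On that view the fault is an undefined test, not proven inflation. This is right as far as it goes, and the 11-14% is conditional on the any-one rule. It does not rescue the plan, because the absence of a rule is itself the defect.

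The correlation ceiling of 0.7 is a choice. Above it the any-one rate drops below 11%, and the all-three rate passes 1%. Even at 0.9, however, the any-one rate is 8.6%.

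Six months is the natural reading of the primary visit: it is when the program ends, and 12 months is called follow-up. That stands, so the six-test figure is only a side scenario. Still, no section names a primary visit, and Study Design does use post-assessment for all of them.

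The analyst is blinded to allocation. That helps only in part: with two-sided tests, an analyst who does not know which arm is which can still see which subtest is below 0.05.

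The trial is small and could report every subtest openly. But the protocol does not call it a pilot. It sets out a formal two-sided primary null, to be tested at 0.05.

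Finally, a lead subtest or an all-three rule would also close the gap. That is true. The documents do not decide between the options, since the null speaks of the battery and the alternative of measures.

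**Conclusion.** The concern holds. The primary hypothesis has no defined test. At 6 months with 12 per arm, the false-positive rate runs from under 1% (all three subtests required) to about 14% (any one suffices). The any-one rate is 11-14% for assumed subtest correlations of 0 to 0.7 and still 8.6-10.0% at 0.8-0.9. The 17-24% figure applies only if 12 months also counts and any one of six tests is enough. None of these figures includes the within-arm paired tests or the switch to a rank-based test, which add further discretion. This must be settled before outcomes are seen, because a rule set afterwards would not be credible.

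**What to change.** Add a short paragraph to Statistics, dated before any outcome is seen:

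- Name 6 months, the end of the intervention, as the sole primary time point.
- Define one BICAMS composite as the mean of the three subtest z-scores, each standardised to the pooled baseline mean and SD. Compare the arms on it once, at two-sided 0.05. This fits the battery-level null.
- If the investigators expect an effect in one domain only, test the three subtests with Holm at a familywise two-sided 0.05 instead. Fix that choice in advance.
- Label 12-month BICAMS and all other outcomes as secondary, reported as estimates with confidence intervals.

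The cost is a few lines of text, with no new data or visits. The statistical price depends on the option. Holm raises the effect detectable on its first step by about 0.2 SD. The composite splits no alpha and does better when all subtests move together, but loses most of its power when only one moves. The investigators should make that choice on the pattern of effect they expect.
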